#### 6.3.2.1 Procedure to monitor adherence

Before delivering the medication to the research subject, the pharmacist must weigh the tubes to be delivered. After the return of the medication by the subject will also carry out the weighing. Guidelines to follow for weighing:

- o The pharmacist will use the scale provided by the sponsor
- o Place the tube in the center of the balance. You will get the result of the measurement.
- o It will remove the tube from the balance and put it back, confirming that the measurement is the same. If it is different, it will weigh one more time and take the average of the 3 measurements
  - o Record the result in the log and the CRF provided by the sponsor

Adherence to the intervention will be calculated considering: the weight of the empty tube, the weight of the strip, the weight of the tube with the content, the calculation of the total gel to be applied during the entire intervention time and the total weight of the applied gel . The following simplified formula will be used:

$$Ad = \frac{\left(P_i - P_f\right)100}{P_T}$$

Where:

Ad = adhesion

 $P_i$  = weight of the tube delivered to the subject at the start

 $P_f$  = weight of the tube returned by the subject

 $P_T$  = weight of the posology indicated for the intervention

$$P_T = (P_g)G$$

where:

 ${\it P_g}$ = weight of a 1 cm strip of the intervention, determined by the research and development department

G = number of applications indicated for the intervention

Adherence will be estimated at each visit where the research subject returns the intervention. Only tubes without apparent physical damage will be considered for the calculation. This result will allow the PI to determine if the subject continues in the study according to the stipulations of the elimination criteria.

The evaluation of the adherence by means of the diary of the subject will be carried out in the following way:

$$Ad = (A_r)100/A_i$$

Ad = Adhesion

 $A_r$ = Registered applications

 $A_i$ = Applications indicated for the intervention

The final (overall) adhesion will be determined by the average of the adherence of each of the visits.

It will not be considered for the calculation of final adherence if the subject did not return the tube in two subsequent visits.

Sophia Laboratories A.S. of V.C.

Version: 1.0

The balance will be provided by Sophia Laboratories, S.A de C.V. You must take shelter in a locked place. It will be placed on a smooth surface (table), avoiding the movement and the change of place as much as possible. The surface of the balance must be kept clean. The maintenance of the same must be according to the manufacturer's specifications. Its use is exclusive for protocol procedures. It is the IP's responsibility to safeguard and correct use.

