#### 6.3 Intervention

# 6.3.1 Managed treatments

# 6.3.1.1 Treatment under study

#### PRO-167

- o Active ingredients: Dexpanthenol 5%
- o Pharmaceutical form: Ophthalmic gel.
- o Prepared by: Sophia Laboratories A.S. of V.C.
- Posology: a strip approximately 1 cm long, 4 times a day during the waking period, in the bottom of the right eye sac.
- Description of the formulation: transparent gel, free of visible particles.
- o Description of the packaging: sterile multi-dose tube, low density polyethylene polyethylene and aluminum with high density polyethylene lid.

Table 3. Quali-quantitative formulation of PRO-167

Type of agent	Amount mg/mL	Function
Dexpanthenol	50.0	Active principle (lubricant)
Boric acid	2.00	Active principle
Sodium Borate decahydrate	without showing	additive
Polysorbate 80	without showing	additive
Sorbitol	without showing	additive
Potassium chloride	without showing	additive
Sodium chloride	without showing	additive
Magnesium Chloride hexahydrate	without showing	additive
Water for the preparation of injectables c.b.p.	1.00	Vehicle

Quali-quantitative formulation of the product under investigation PRO-167. The concentration of the active principles is shown, as well as the substances that act as a buffer additive.

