#### 6.3.2 Strategies to improve adherence and procedure to monitor adherence

- 1. Each visit the research subject will return the assigned tube in order to evaluate the adherence by weigh
- 2. Direct questioning by the PI about the application of the intervention.

- 3. At the discretion of the IP, messages may be sent or reminder calls made.
- 4. Delivery of a printed chronogram specifying the date of the visit and its activities
- 5. Journal of the subject.

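### Overall adherence is a plain average of two visit scores whose intervals are never equal and whose denominators carry no visit index, so it can misstate total use at the >60% analysis gate (minor)

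*Combined protocol and SAP*

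**What the plan says.** All references are to the combined protocol and SAP.

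- **When adherence is scored.** Section 6.3.2.1: "Adherence will be estimated at each visit where the research subject returns the intervention". Sections 6.3.4.1 and 6.3.4.3 have gel handed out at baseline and visit 1 and brought back at visit 1 and the final visit, so there are two scores.
- **How each score is formed.** By weight, the gel used is divided by P_T, the weight of a 1 cm strip times G, where G is the "number of applications indicated for the intervention". By diary, registered applications are divided by A_i, defined in the same way. The lead-in to the weight formula speaks of "the calculation of the total gel to be applied during the entire intervention time and the total weight of the applied gel". None of these terms is tied to a visit.
- **How the scores are combined.** "The final (overall) adhesion will be determined by the average of the adherence of each of the visits". No weighting is given.
- **What the scores feed.** The visit score bears on continuation: "This result will allow the PI to determine if the subject continues in the study according to the stipulations of the elimination criteria". Section 6.2.3 sets that line at adherence below 50% by diary. Section 8.3.1 admits subjects above 60% to the analysis that serves the study objective. It does not name the measure, but the overall score is the natural input.
- **Schedule.** Application is "4 times a day during the waking period" (6.3.1.1) for 10 days (section 1), starting the day after baseline (6.5.1.2). Visit 1 is on day 3 ± 1 and the final visit on day 11 ± 1 (6.4.4).

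**The concern.** A plain average of two rates equals the overall rate only if both rest on the same number of due applications or the two rates are equal. Here the first interval is always much the shorter, so each application before visit 1 counts for more than each one after it. A subject who starts well and then slackens is scored too high against total use, and one who starts badly and then improves is scored too low. Some such subjects cross the >60% line in the direction opposite to their total use. With 12 subjects per group, one misplaced subject is 1/12, about 8% of an arm.

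The missing visit index is the more basic gap. If the denominator is the whole course at each visit, neither the visit scores nor their average measures adherence at all, and the visit 1 score is the one that reaches the continuation decision.

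**Working it through.** The plan states no worked adherence figure, so there is none to reproduce.

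**Inputs.** Total due = 4 per day x 10 days = 40, assuming all 40 fall before the final visit. Let a be the number due before visit 1. Dosing starts on day 1 and visit 1 is on day 2, 3 or 4. So a runs from 4 (day 2, before that day's doses) to 16 (day 4, after them). On day 3 it is 8 to 12; a = 12 assumes that all day-3 doses precede the visit. An equal 20/20 split cannot occur.

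**Step 1: denominators read literally (40 at each visit), perfect user.**
- Separate tube or diary per interval: [a/40 + (40 - a)/40]/2 = 50% for every a. The visit 1 score is a/40, that is 10% to 40%.
- One tube weighed against its baseline weight: (a/40 + 1)/2 = 55% at a = 4 and 70% at a = 16.

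**Step 2: denominators per interval.** Let Ad1 and Ad2 be the interval scores.

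Plain average minus total use = (Ad1 + Ad2)/2 - [a Ad1 + (40 - a) Ad2]/40 = (0.5 - a/40)(Ad1 - Ad2).

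At a = 12 the difference is 0.2 x the gap:
- 9/12 and 14/28: average (0.75 + 0.50)/2 = 62.5%, included; total 23/40 = 57.5%, not above 60%.
- 6/12 and 19/28: average (0.500 + 0.679)/2 = 58.9%, excluded; total 25/40 = 62.5%, above 60%.

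**Step 3: how many use patterns change status.** All whole-number pairs (x of a, y of 40 - a) were listed, and the average was compared with (x + y)/40 at the >60% line. This was done with and without a floor of 50% in each interval. At a = 12 the floor leaves 7 x 15 = 105 pairs; without it there are 13 x 29 = 377.

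| Split | Coefficient | With floor: changed (in by average only / out by average only) | Total use of those | No floor: changed | Total use of those |
|---|---|---|---|---|---|
| 4/36 | 0.4 | 10 of 57 (7/3) | 52.5-67.5% | 44 of 185 | 30-90% |
| 8/32 | 0.3 | 9 of 85 (7/2) | 55-65% | 54 of 297 | 37.5-82.5% |
| 12/28 | 0.2 | 6 of 105 (5/1) | 57.5-62.5% | 49 of 377 | 45-75% |
| 16/24 | 0.1 | 3 of 117 (3/0) | 60% | 28 of 425 | 52.5-67.5% |

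The six at 12/28 with the floor are (8,15), (8,16), (9,14), (9,15) and (10,14), in by the average only, and (6,19), out by the average only. Three of them, (8,16), (9,15) and (10,14), total exactly 24/40 = 60.0% and change status only because the gate is a strict >60%. All three at 16/24 are such ties. Without the floor, the extremes at 12/28 are 12/12 with 6/28 (average 60.7%, total 45%) and 2/12 with 28/28 (average 58.3%, total 75%).

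These are counts of possible patterns, not probabilities. The documents give no adherence distribution.

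**The case against.** **The rule is prespecified.** Overall adherence is defined as the average of the visit scores, and 8.3.1 does not say that its 60% means a share of all applications. A reader might infer an arithmetic error in the plan, but nothing is mis-added and no stated figure fails. What stands is that the chosen score does not measure total use, and that the plan offers no reason to count early applications more heavily.

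**The literal denominator is not what was meant.** A reader might infer that no subject could pass the gate. The documents do not support that: 6.3.4.1 supplies gel in stages for the period each delivery covers, which points to per-interval scoring. What stands is that 6.3.2.1 does not say so, and that "Each visit the research subject will return the assigned tube" (6.3.2) leaves open whether the tube from visit 1 onward is new. With one tube and cumulative denominators, the final score would already be total use. Averaging it with the visit 1 score would then leave a difference of 0.5 x (1 - a/40) x the gap, or 0.35 x the gap at 12/28. So that reading does not remove the problem.

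**The effect is small.** Half of the changes at 12/28 with the floor are exact ties, and the other three are one application from 60%. Section 8.3.1 also justifies its gate by a minimum of 1 cm per day. With the floor, the lowest total among changed patterns is 52.5%, or 21 applications, about 2.1 per day. Whole-number patterns fit the diary; weight is continuous. All of this stands and limits the severity.

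**Only users near 60% are affected.** A reader might infer this, but it holds only if the 50% rule is applied in each interval. Section 6.2.3 names the diary and does not say per visit. Section 6.3.2.1 suggests use at each visit, but places that after the weight formula. Without the floor, subjects totalling 45% to 75% can change status at 12/28.

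**Conclusion.** The point holds as a minor defect with two linked parts. The denominators lack a visit index. On the per-interval reading, the plain average departs from total use by (0.5 - a/40) times the gap between interval scores, a coefficient of 0.1 to 0.4 across the visit 1 window. At 12/28, 6 of 105 patterns change status if the 50% rule applies in each interval, and 49 of 377 if it does not.

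This rests on four assumptions: 40 applications due before the final visit (whose window opens on day 10); per-interval denominators; the overall score as the input to the >60% gate; and, for 12/28, all day-3 doses taken before visit 1.

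A reader might infer that the study's safety conclusions are at risk. The documents do not support that. A subject with equal use in both intervals has no error. The intent-to-treat set (8.3.3) and the adverse event report (8.3.1) have no adherence gate. The averaging does not touch any single-visit continuation decision; only the missing visit index does. No rate of misclassification can be estimated from the documents.

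**What to change.** In 6.3.2.1:

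1. Define G (and so P_T) and A_i at each visit as the applications due in that dispensing interval.
2. Replace the plain average with a pooled ratio: total registered applications / total due x 100 for the diary, or total gel weight used / (P_g x total due) x 100 for weight.
3. Sum over evaluable intervals only. The section already says "Only tubes without apparent physical damage will be considered for the calculation", so an interval with a damaged or unreturned tube should leave both numerator and denominator.
4. State whether the tube delivered at visit 1 is new or the same one reweighed.

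The sponsor should also reconcile which measure (diary or weight, per visit or overall) 6.2.3, 6.3.2.1 and 8.3.1 use. No threshold is proposed here.

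The cost is a short rewrite of 6.3.2.1 and matching wording in the other two sections. Tube weights and diaries are already collected at both visits, so no new data are needed. The change should be made before the database is frozen, so that the formula is not chosen with adherence data in view.

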#### **Duration of treatment**: 10 days

#### Reference product, dose and route of administration, lot:

- Corneregel®. Dexpanthenol 5%. Ophthalmic gel developed by Bausch & Lomb, Berlin, Germany.
  - Dose: a strip approximately 1 cm long, 4 times a day during the period of vigil, in the bottom of the right eye sac.
  - Route of administration: ophthalmic

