#### 6.3.4.3 Return

The research subjects will return to the staff indicated by the IP in the center their treatments in visits 1 and final. The refund will be made by the research center when the sponsor indicates it. Prior to the return the research center must make a count of the assigned medication and the remaining medication, with the aim of creating an inventory which serves for the final filling of the return form of the medication.

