#### 6.5.1.2 Basal visit

- Review of laboratory tests: refers to the review and analysis by the IP of the results of the BH, QS and PFH. See 6.4.3.12 Laboratory tests.
- Eligibility criteria: with the laboratory results, the subject's profile will be finalized for inclusion or not.
- Assignment: It refers to determining the intervention that the patient will follow during the study. It will be done according to section 7. Methods. Assignment of the intervention. This assignment will be made at the baseline visit (day 0) and will go along with the indication to start the treatment period the next day (day 1).
- Delivery of intervention: Refers to the delivery of the product under investigation to the patient of the study, by the research center. It will be done according to sections 6.3.1 Managed treatments and 6.3.4.1 Delivery and reception.
- Evaluation of variables: The data of the evaluation of the variables listed below can be taken from the scrutiny visit, as long as it does not exceed 7 days prior to this visit. It is the IP's prerogative to decide whether to use the information from the screening visit or to repeat the evaluations on this visit.
  - o Intraocular pressure
  - o Visual capacity
  - o TRL
  - o Epithelial defects (TF and TVL)
  - o Eye signs and symptoms
  - o Subsequent segment
  - o vital signs

- Eye comfort index: see 6.4.3.3 Eye comfort index
- Density of goblet cells (cytology per impression): see 6.4.3.2 Density of goblet cells (cytology per impression)
- Delivery of the subject's diary: It refers to the delivery by the IP to the subject, the subject's daily instrument.
- Delivery of quality questionnaire: It refers to the delivery by the IP to the subject, the quality questionnaire instrument.

#### 6.5.1.3 Visit 1

- Intervention delivery: see 6.5.1.2 Baseline visit
- Return of intervention: refers to the return of research products to the center by the research subject.
- Evaluation of adherence: refers to the assessment made by the IP according to section 6.3.2.1 Procedure to monitor adherence
- Adverse events: see 6.4.3.5 Presence of adverse events
- Intraocular pressure: see 6.4.3.6 Intraocular pressure
- Visual ability: see 6.4.3.1 Visual capacity
- TRL: see 6.4.3.10 Rupture time of the tear film
- Epithelial defects (TF and TVL): see 6.4.3.4.1 Stains
- Eye signs and symptoms: see 6.4.3.4 Eye surface integrity: and 6.4.3.9 Ocular symptomatology

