Those subjects who comply with an adherence greater than 60% will be included in the statistical analysis to meet the objective of the study. It was considered that from the minimum dose necessary to obtain a pharmacological effect (reepithelizer / 1 cm per day) and the presence of adverse events (exposure) is sufficient to meet the overall design objective, according to the pharmacological characteristics of the product in investigation.

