#### CONFIDENTIAL

- Subject security
- Alteration of the risk-benefit balance
- Commit the integrity of the study data
- Affects the voluntariness of the subject in the participation of the study.

The list of examples cited below serves the purpose of guidance, but does not cover all possible cases, so it is not limiting:

- I. In relation to informed consent: 1) that informed consent has been taken by an unauthorized person to do so, 2) that the subject under investigation signs a version of informed consent not approved by the committees and regulatory entity, 3) that perform a study procedure prior to signing informed consent.
- II. Regarding the inclusion / exclusion criteria: 1) enroll subjects who do not meet all the inclusion criteria and / or meet any exclusion criteria, 2) enroll defined subjects as part of the so-called vulnerable population: children, pregnant women, prisoners, without prior approval for such group; 3) Enroll patients before the start or after the end of the study.
- III. In relation to the medication of the study: error in the delivery or dosage of the same.
- IV. In relation to concomitant medication: use of prohibited medication.
- V. **In relation to the study procedures:** that those that, in the opinion of the principal investigator, compromise the safety of the research subject are not carried out.
- VI. **In relation to the reporting of serious adverse events**: those that are reported outside the time stipulated by the committees.

Minor desviation: is that which does not impact on the safety of the subject, does not alter the risk-benefit balance, does not compromise the integrity of the study data or does not affect the subject's willingness to participate in the study.

The list of examples cited below serves the purpose of guidance, but does not cover all possible cases, so it is not limiting:

- I. Oblivion in the taking of the study medication.
- II. Lack of return of study medication by the subject.
- III. Visits of the research subject carried out outside the window.

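### Final weight adherence has no workable rule for a missing tube: if the >60% gate uses it, 12 of 40 applications can score 100%, while a complete diary with no tubes has no weight score

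*Combined protocol and SAP*

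**What the plan says.** Section 6.3.2.1 defines two adherence measures.

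- **Tube weight:** the weight lost from the tube, divided by the weight of gel indicated. Timing is by return: "Adherence will be estimated at each visit where the research subject returns the intervention". Tubes with visible damage are left out of the calculation.
- **Diary:** applications recorded, divided by applications indicated.

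Final adherence is the average of the visit values. The sentence saying so follows the diary formula and does not say which measure is averaged. Next comes the only rule on non-return: "It will not be considered for the calculation of final adherence if the subject did not return the tube in two subsequent visits".

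Section 6.3.4.3 fixes the number of returns: "The research subjects will return to the staff indicated by the IP in the center their treatments in visits 1 and final". The schedule in 6.5 agrees, and has the diary returned and evaluated at the same two visits.

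Section 8.3.1 sets the gate: "Those subjects who comply with an adherence greater than 60% will be included in the statistical analysis to meet the objective of the study". It does not say whether weight or diary is meant. The elimination criterion in 6.2.3 (adherence below 50%) names the diary, yet 6.3.2.1 says the weight result informs whether a subject continues under the elimination criteria. Section 8.3.3 defines an intention-to-treat set by completion of the baseline visit and Visit 1, with no adherence condition.

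**The concern.** With two return visits, a rule for two missed returns says only what happens when every tube is missing. For one missing tube the text is silent. Since an estimate is made only where a tube is returned, the natural inference is that the remaining visit value stands for the whole course. For a damaged tube the exclusion is explicit.

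The direction of error matters. Section 8.3.1 calls the product safe and tolerable when no clinical and statistical differences from the comparator are found on the primary outcomes, and it gives the >60% set the task of meeting the study objective. A subject who stopped early but is scored as fully adherent dilutes exposure in that set. A well-exposed subject whose tubes are lost has no weight score with which to enter it. With 12 subjects per group, each misclassified subject is 1/12, or 8%, of a group.

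**Working it through.** **Inputs**

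- Four applications a day: "a strip approximately 1 cm long, 4 times a day during the waking period, in the bottom of the right eye sac" (6.3.1.1).
- "Duration of treatment: 10 days" (Summary), starting on day 1, the day after baseline (6.5.1.2).
- Visit 1 on day 3 ± 1 (6.4.4).
- Total indicated: 4 × 10 = 40. The documents do not print this figure.
- Split at day 3: 4 × 3 = 12, then 40 − 12 = 28. Over the window it is 8 + 32 (day 2) to 16 + 24 (day 4), counting whole days.

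The plan gives no adherence result to reproduce.

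**Formulas in 6.3.2.1.** Weight: Ad = 100 (Pi − Pf)/PT, with PT = Pg × G. Diary: Ad = 100 Ar/Ai. Final = unweighted mean of the visit values. The examples assume each strip has its nominal weight, so weight adherence equals applications used over G.

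**Step 1: which G?** The text defines G as the applications indicated for the intervention and also mentions gel for the whole intervention time, so G = 40 at each visit is a possible reading. A perfect user returning both tubes would then score 12/40 = 30% and 28/40 = 70%, a mean of 50%. That mean is 50% wherever Visit 1 falls. Nobody who returns both tubes and uses no more than indicated could exceed 60%, and a perfect user would stand at 30% at Visit 1. Only a per-interval G (12, then 28) works with averaging and a 60% gate.

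**Step 2: 12 of 12, then 0 of 28, no usable second tube.** True use is 12/40 = 30% (8/40 = 20% to 16/40 = 40% over the window).

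| Reading | Score | Passes >60%? |
|---|---|---|
| Weight, per-interval G, missing visit skipped | 12/12 = 100% | Yes |
| Weight, missing visit scored 0 | (100 + 0)/2 = 50% | No |
| Weight, G = 40 | 12/40 = 30% | No |
| Truthful diary, pooled | 12/40 = 30% | No |
| Truthful diary, averaged by visit | (100 + 0)/2 = 50% | No |

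**Step 3: how wide is the gap on the first reading?** After 12 of 12, pooled use exceeds 60% only above 24/40, that is, with more than 12 of the 28 remaining applications (43%). At or below that, the subject still scores 100%. Even 8 of the first 12 (66.7%) and nothing after would pass, with true use of 8/40 = 20%.

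**Step 4: the opposite error.** A subject with 12/12 then 16/28 who returns only the second tube scores 16/28 = 57.1% and fails; true use is 28/40 = 70%. A subject with 40/40 in the diary and no tubes has no final weight score, although the diary gives 100%.

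**Step 5: both tubes returned.** The unweighted mean still distorts: 12/12 and 0/28 average 50% against a true 30%.

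**The case against.** The strongest reply is that the 100% score depends on a chain of readings. Much of that stands.

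- **Skipping one missing tube.** A reader might infer that the protocol states a rule to skip any interval without a tube. It does not: the sentence concerns two missed returns, and skipping one is an inference. Scoring it 0 gives 50% and a fail. But no sentence scores it 0 or fills it from the diary either, and for damaged tubes the exclusion is stated.
- **Denominator.** Ambiguous as worded, but the whole-course reading fails on its own terms (step 1).
- **The diary.** A reader might infer that a full user without tubes has no adherence score at all. Only the weight score is missing. A truthful diary gives that subject 100%, and gives the low user 30% or 50%. The opening of "It will not be considered for the calculation of final adherence if the subject did not return the tube in two subsequent visits" could even mean that weight is dropped and the diary remains. The text does not say so, and nowhere makes the diary a substitute.
- **The gate.** Section 8.3.1 names no measure, so its use of the weight score is an assumption. The final score of 6.3.2.1 is, however, the only overall adherence the protocol defines.
- **Consequences.** A reader might infer that such subjects are lost to the study. Adverse events are reported for all randomised participants (8.3.1), and the intention-to-treat set has no adherence condition.
- **Frequency.** It is tempting to say that those who stop the gel are those who fail to return tubes. The documents give no data on this, and 6.3.2 adds questioning by the investigator and optional reminders.
- **Section 10.5.** It lists "Lack of return of study medication by the subject" as a minor deviation, a class defined as not compromising data integrity. That sits awkwardly with a return-based score, but the examples are only guidance, so little rests on it.

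**Conclusion.** The point holds in limited form. Section 6.3.2.1 leaves a single missing tube without a stated rule and gives no final weight score when both are missing. On the only workable denominator, if the missing visit is skipped and the >60% gate uses this score, 12 of 40 applications can count as 100% against a true 30% (20% to 40% over the Visit 1 window). A subject with a complete diary and no tubes has no final weight score.

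The effect is limited to the >60% analysis set. The documents support no estimate of how many subjects would be affected; 8% of a group is the weight of one subject, not an expected bias. It is still worth correcting before analysis, because membership of the set assigned to the study objective can turn on whether a tube was brought back, while a second record covering the same days is already collected.

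**What to change.** In 6.3.2.1:

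- For any interval without a usable tube (not returned or damaged), use the diary count of applications for that interval.
- Compute final adherence as total applications over both intervals divided by the total indicated, 40. For a returned tube, applications are (Pi − Pf)/Pg.
- Delete the two-visit sentence.
- State what happens if the diary for that interval is missing too.

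In 8.3.1, state that the >60% gate uses this measure, and say how the gated set relates to the intention-to-treat set in 8.3.3. The measure must also be reconciled with the diary-based criterion below 50% in 6.2.3 and with the statement in 6.3.2.1 that the weight result informs continuation.

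Given a truthful diary, the early stopper scores (12 + 0)/40 = 30%, the subject with 12 then 16 scores 28/40 = 70%, and the full user without tubes scores 40/40 = 100%. Pooling also removes the distortion in step 5, and the denominator stays 40 wherever Visit 1 falls.

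The cost is a few sentences and no new data collection. The downside is that a substituted interval rests on self-report, so the report should give the number of such intervals by group.
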